PROTOCOL TITLE:

Mapping Electrogram Morphology Recurrence for Atrial Fibrillation Ablation

PRINCIPAL INVESTIGATOR:

[name]
Department of Medicine, Cardiovascular Division
[name]
[name]
[contact]
[contact]

VERSION NUMBER:

2.6

VERSION DATE:

15 November 2019

NCT #: **NCT03082963**

Table of Contents

1.0 Objectives	3
2.0 Background.....	3
3.0 Inclusion and Exclusion Criteria	4
4.0 Study-Wide Number of Subjects	4
5.0 Study-Wide Recruitment Methods	4
6.0 Multi-Site Research	4
7.0 Study Timelines	4
8.0 Study Endpoints.....	5
9.0 Procedures Involved	6
10.0 Data and Specimen Banking.....	9
11.0 Data Management.....	9
12.0 Provisions to Monitor the Data to Ensure the Safety of Subjects.....	10
13.0 Withdrawal of Subjects*.....	14
14.0 Risks to Subjects*	15
15.0 Potential Benefits to Subjects	17
16.0 Vulnerable Populations.....	17
17.0 Multi-Site Research	17
18.0 Community-Based Participatory Research.....	17
19.0 Sharing of Results with Subjects	17
20.0 Setting	17
21.0 Resources Available	17
22.0 Prior Approvals.....	18
23.0 Recruitment Methods.....	18
24.0 Local Number of Subjects	18
25.0 Confidentiality	18
26.0 Provisions to Protect the Privacy Interests of Subjects	18
27.0 Compensation for Research-Related Injury.....	19
28.0 Economic Burden to Subjects.....	19
29.0 Consent Process	19
30.0 Process to Document Consent in Writing.....	20
31.0 Drugs or Devices	20

1.0 **Objectives**

The overall goal of this early feasibility project is to test the feasibility and safety of performing real-time electrogram morphology recurrence (EMR) mapping in patients with persistent atrial fibrillation (AF) to locate areas of high electrogram morphology recurrence rate. We believe that the EMR mapping can be integrated into cardiac mapping and used to identify potential sites for ablation. Furthermore, this study could provide preliminary data on the efficacy of this technology's ability to terminate or slow AF.

We will test this technology on ten subjects undergoing a second ablation procedure. We will map the AF utilizing the EMR to indicate locations of stable activity. This information will be provided to the cardiac electrophysiologist performing the procedure to integrate with the other electroanatomic data to develop an ablation strategy focused on ablating the drivers for AF. By targeting these drivers, we hypothesize that we can produce acute AF termination or AF cycle length prolongation. In addition to testing the real-time electrogram morphology recurrence mapping, we would also like to determine the acute effects of radiofrequency ablation of areas of high recurrence rates and determine long term freedom from AF following ablation of areas of high recurrence rates.

2.0 **Background**

Atrial fibrillation (AF) (an abnormal, rapid heart rhythm coming from the upper chambers of the heart [atria]) is the most common type of heart rhythm disorder or arrhythmia (abnormal heart rhythm). Instead of the heart beating in a steady pattern, in AF the upper chambers of the heart (atria) quiver rapidly in an unsteady manner. Atrial fibrillation may be treated with drug therapy designed to either prevent the heart rate from going too fast during atrial fibrillation (rate control therapy) or with drug therapy designed to stop the abnormal rhythm and maintain normal heart beating (rhythm control therapy). Atrial fibrillation may also be treated with catheters inserted into blood vessels that can be placed inside the heart to eliminate the critical zones or triggers for atrial fibrillation or stop those conditions that keep it going (catheter ablation). It is not known how to best locate these critical zones or triggers to be targeted by catheter ablation.

The aim of this study is to investigate a recently developed electrogram mapping technique for AF, known as an electrogram morphology recurrence (EMR) analysis. This technique identifies areas of the atria that have high rates of electrogram morphology repeatability that may be characteristic of AF sources. This non-linear technique uses cross-correlation of AF activation waveforms to determine the frequency of the most common waveform morphology. In a pilot study of patients who underwent ablation targeting the PVs, electrograms with highest recurrence rates located in the left atrium predicted ablation success. In contrast, having these fast/repeatable electrograms in the right atrium indicated a very poor ablation (performed in the left atrium) success rate (0%). Additionally, in a canine rapid atrial pacing model of AF, EMR was able to identify AF rotors. Although these preliminary studies suggest that areas of high rates of EMR may play a role in AF persistence, it is unknown if mapping of these sites can be used to direct treatment (i.e. ablation).

3.0 Inclusion and Exclusion Criteria

Approximately fifteen (15) subjects will be recruited from the University of Miami. Patients will be screened for participation in this study by the investigator or his clinical staff for inclusion. The study aims to complete ten (10) participants through the ablation procedure and a minimum of one (1) year follow-up.

INCLUSION CRITERIA:

- Male and female, at least 21 years of age
- Subjects with persistent AF with one prior failed ablation for persistent or long standing persistent AF

EXCLUSION CRITERIA:

- Inability to sign consent.
- Patients with a life expectancy <1 year.
- Patients with chronic kidney disease with sufficiently low GFR that precludes either CT angiogram of the heart or contrast MRI study.
- Patients with contraindications to catheter ablation for atrial fibrillation (i.e. left atrial thrombus, class IV heart failure, etc)
- Pregnant women and women that are breast feeding
- Patients with multiple (2 or more) prior failed ablations.
- Patients who have had chemotherapy or radiotherapy within 4 weeks prior to entering the study or those who have not recovered from adverse events due to agents administered more than 4 weeks earlier.

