7.0 Study Timelines

The research subjects will be undergoing a clinically-indicated second ablation procedure. On the day of the ablation procedure, the procedure will be utilizing the new mapping technology to identify areas of high EMR and this information will be incorporated into the ablation strategy in conjunction with the other electroanatomic data. As is the usual

clinical routine, patients will be followed every 3-12 months after completion of (or early withdrawal from) study treatment, as clinically indicated, for a minimum of one year.

Upon completion of all study data collection on the 10 participants, primary data analysis will begin.

Follow-up. The patients will undergo standard post ablation follow-up as part of their routine clinical care. As per the Heart Rhythm Society guidelines, following ablation, patients receive some type of post ablation monitoring (Event monitor, Holter monitor, smartphone monitor, Implantable loop recorder-LINQ). This choice of monitoring will be made by the patient's physician in conjunction with the patient based on clinical need. The follow-up schedule will also be determined based on patient and clinical need, and the guidelines. The following table presents an idealized version of the follow-up schedule, but this will be adjusted based on clinical need.

	Screening	Day 0	5-28 days post	2-4 months post	4-8 ³ months	10-14 months
H&P	X	X	X	X	X	X
ECG	X	X	X	X	X	X
Labs	X ⁴	X ⁵				
Monitoring ¹					X	X
Device Interrogation ²	X	X	X	X	X	X

1 Monitoring information will be collected if ordered for standard clinical care. This includes Ambulatory monitoring (Holter), Event Monitor, SmartPhone Monitor

2 Device Interrogation will be performed as part of standard clinical care. This includes implantable loop recorder (LINQ), pacer or defibrillator, if the patient has a device

3 If a patient does not have an office visit in this window, a phone follow-up will be obtained.

4 Labs are clinically indicated and include basic metabolic panel for screening

5 Labs are clinically indicated and include basic metabolic panel, CBC and coagulation panel and may be performed within 3 weeks prior to the procedure

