8.0 Study Endpoints

Feasibility of performing real-time electrogram morphology recurrence maps will be determined to assess if maps show specific areas of high morphology recurrence.

The acute effects of ablation will be classified as either causing AF termination, AF slowing, or no change. We will identify the number of subjects in each category.

In addition, we will collect 30 day safety endpoints that may occur after the ablation using the following Table and then categorize whether the AE/SAE is related to the procedure.

Adverse Events during or attributable to the Ablation Procedure

TYPE OF AE	Grade	Attribution categories
Adverse Event vs. SAE 
 • cardiac perforation • cardiac tamponade • Vascular • Pulmonary • Proarrhythmia • Phrenic nerve paralysis (lasting > 24 hours) • Pulmonary Vein Stenosis • GI bleed • CVA • TIA • MI • Infection • Allergic reaction during procedure • CHF • Syncope/near syncope • GI/Esophageal complications 	
Mild (grade 1): the event causes discomfort without disruption of normal daily activities.
 
Moderate (grade 2): the event causes discomfort that affects normal daily activities.
 
Severe (grade 3): the event makes the patient unable to perform normal daily activities or significantly affects his/her clinical status.
 
Life-threatening (grade 4): the patient was at risk of death at the time of the event.
 
Fatal (grade 5): the event caused death
	
Definite – The AE is clearly related to the study.
 
Probable – The AE is likely related to the study.
 
Possible – The AE may be related to the study treatment.
 
Probably unrelated- The AE is likely not related to the study
 
Unrelated – The AE is clearly NOT related to the study.

A “serious” adverse event is defined in regulatory terminology as any untoward medical occurrence that:

- **Results in death.**

If death results from (progression of) the disease, the disease should be reported as event (SAE) itself.

- **Is life-threatening.**

The patient was at risk of death at the time of the event; it does not refer to an event that hypothetically might have caused death if it were more severe.

- **Requires in-patient hospitalization or prolongation of existing hospitalization for ≥ 24 hours.**
- **Results in persistent or significant disability or incapacity.**
- **Is an important medical event**

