will be remapped a second time to determine if another potential source still exists. If so, additional ablation will be performed at that site. After ablation based on the morphology recurrence plot, if AF has not terminated, *physician discretion will determine whether further EMR mapping guided ablation or further “standard” ablation will be performed as per physician protocol.* AF termination will be diagnosed if either sinus rhythm is restored with ablation or a regular atrial tachycardia or flutter ensues. Stable coronary sinus recordings will be used to assess ablation-induced slowing using the real-time software. The 3-D position of each ablation lesion will be documented.

10.0 **Data and Specimen Banking**

No biological specimens will be collected or stored for this research.

The data that will be stored includes demographic/clinical information on the research subject and the data from the EMR protocol. Please see section 11 for more information on the length of storage, location, access, etc. Any data requests from outside parties may also be submitted via written request to the PI and all data will be de-identified prior to release.

11.0 **Data Management**

Data Analysis

Clinical Data: Demographic and clinical data will be tabulated as means and standard deviations for continuous variables and counts with percentages for categorical variables.

For EMR Data: We will compare the cycle length prolongation seen with EMR ablation to that seen in a cohort of age and sex matched patients selected from our database of patients who have undergone a second AF ablation procedure for persistent AF with conventional methods. We will also compare acute termination rates and procedure duration. A difference of 10% in cycle length slowing between recurrence-based ablation vs. conventional ablation can be detected with 10 patients per group with 0.89 power. We will define a successful Phase I as AF termination or cycle length slowing of the coronary sinus of at least 15% in at least 7 of 10 patients from morphology recurrence mapping directed ablation.

Data Confidentiality

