13.0 Withdrawal of Subjects

Patients can be taken off the study at any time at their own request, or they may be withdrawn at the discretion of the investigator for safety, behavioral or administrative reasons. The reason(s) for discontinuation will be documented and may include:

- Patient voluntarily withdraws from treatment (follow-up permitted);
- Patient withdraws consent (termination of treatment and follow-up);
- During the mapping and ablation procedure, if the patient is not deemed sufficiently stable to perform the research mapping procedure;
- Patient is unable to comply with protocol requirements;
- Patient experiences toxicity that makes continuation in the protocol unsafe;

- Treating physician judges continuation on the study would not be in the patient's best interest;
- Lost to follow-up. Example language: If a research subject cannot be located to document survival after a period of 1 year, the subject may be considered "lost to follow-up." All attempts to contact the subject during the one years must be documented.

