24.0 Local Number of Subjects

Approximately fifteen (15) subjects will be enrolled in this study and screened for participation in this study. Ten (10) participants found eligible for the trial will receive the ablation procedure and then will be followed every 3-12 months, as clinically indicated, after completion of (or early withdrawal from) study treatment, for a minimum of one (1) year. These ten patients will be matched with a cohort of age and sex matched patients who have undergone a second AF ablation procedure for persistent AF with conventional methods.

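### Do Sections 3.0 and 24.0 define the ten patients differently, so that a withdrawal during the procedure could tip the 7-of-10 rule?

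*Combined protocol and SAP*

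**What the plan says.** Section 3.0 gives the recruitment target: about fifteen recruited, and "The study aims to complete ten (10) participants through the ablation procedure and a minimum of one (1) year follow-up". Section 24.0 also has about fifteen enrolled and screened, then states "Ten (10) participants found eligible for the trial will receive the ablation procedure"; these patients "will be followed every 3-12 months, as clinically indicated, after completion of (or early withdrawal from) study treatment", for at least one year. Section 7.0 sets the time of analysis: "Upon completion of all study data collection on the 10 participants, primary data analysis will begin".

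Section 11.0 (Data Analysis) defines a successful Phase I as AF termination, or coronary sinus cycle length slowing of at least 15%, "in at least 7 of 10 patients from morphology recurrence mapping directed ablation". Section 13.0 says of patients that "they may be withdrawn at the discretion of the investigator for safety, behavioral or administrative reasons", and one listed reason is "During the mapping and ablation procedure, if the patient is not deemed sufficiently stable to perform the research mapping procedure". Reasons for discontinuation are to be documented. The feasibility endpoint in Section 8.0 is descriptive: "Feasibility of performing real-time electrogram morphology recurrence maps will be determined to assess if maps show specific areas of high morphology recurrence".

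No section names an analysis set, says whether a withdrawn patient is replaced, or says how that patient is scored.

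**The concern.** Section 3.0 can be read as ten completers drawn from about fifteen recruits, so that a patient withdrawn in the laboratory is not one of the ten and another is enrolled. Section 24.0 can be read as ten treated patients with early withdrawals retained, so that the same patient stays and cannot be a success.

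With a fixed bar of 7, one patient can decide the verdict. Suppose six of nine patients succeed and the tenth is withdrawn. Kept, the result is 6/10 and the rule is not met. Replaced by a patient who succeeds, it is 7/10 and the rule is met. The study is open and the outcome is known on the day of the procedure, so the choice could be made with the running count in view. Section 3.0 also mentions one-year follow-up in the same sentence as the ten, which might seem to let late losses alter an acute result.

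**Working it through.** **The passages side by side.** Section 3.0 states an aim: ten through ablation and a year of follow-up. Section 24.0 has ten ablated and followed for at least a year. These are the same ten patients. The clause about early withdrawal does not set Section 24.0 apart, because it also appears in Sections 7.0 and 9.0, each time as part of the visit schedule.

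Neither supposed reading follows from its own section:

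- A patient too unstable for research mapping may never have received the ablation, so Section 24.0 does not establish that the patient stays among the ten.
- The ablation is clinically indicated (Section 7.0), and Section 13.0 permits follow-up after withdrawal from treatment. A patient withdrawn only from research mapping could still be ablated and followed for a year, so Section 3.0 does not establish that the patient leaves.

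**The plan's own figure.** The only stated operating figure is power of 0.89 for a 10% difference with 10 per group. It belongs to the matched comparison and comes without an SD, alpha or sidedness, so it cannot be checked independently. A two-sided 5% t-test gives 0.89 if the SD is about 6.6 points. On that basis power is 0.85 with 9 per group and 0.80 with 8. No error rate or power is stated for the 7-of-10 rule.

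**Given one withdrawal among the first ten.** Response rates p are assumed. Kept as a non-success, 7 of the other 9 must succeed; replaced, 7 of 10 must succeed.

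| p | Kept: P(X≥7), n=9 | Replaced: P(X≥7), n=10 | Difference |
|---|---|---|---|
| 0.60 | 0.232 | 0.382 | 0.15 |
| 0.70 | 0.463 | 0.650 | 0.19 |

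The difference is P(exactly 6 of 9) × p: 0.251 × 0.60 = 0.15 and 0.267 × 0.70 = 0.19.

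**Averaged over whether a withdrawal happens.** With withdrawal probability a per patient, the kept rule gives P(X≥7) with n=10 and success probability p(1−a). The documents give no withdrawal rate. The 2-3% below is the serious-complication risk in Section 14.0, a different quantity used only as a low reference; 5% and 10% are assumed.

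| a | Chance of at least one in ten, 1−(1−a)^10 | p=0.70: kept (shift from 0.650) | p=0.60: kept (shift from 0.382) |
|---|---|---|---|
| 2% | 0.18 | 0.612 (0.038) | 0.353 (0.029) |
| 3% | 0.26 | 0.593 (0.057) | 0.338 (0.044) |
| 5% | 0.40 | 0.555 (0.095) | 0.310 (0.072) |
| 10% | 0.65 | 0.460 (0.190) | 0.245 (0.137) |

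**What the data would say either way.** Exact 95% intervals are 26-88% for 6/10 and 35-93% for 7/10. The estimates are barely distinguishable; only the label changes. For feasibility, 9/10 (56-100%) against 10/10 (69-100%) changes no verdict, because Section 8.0 sets no threshold.

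**One-year follow-up.** The acute outcome is fixed on the procedure day, and no section removes a patient lost later from the acute count. Even if such patients were removed, equal loss would cause no shift. A shift needs assumed unequal loss: with 10% of responders and 20% of non-responders lost, the response rate becomes 0.70×0.90/(0.70×0.90+0.30×0.80) = 0.63/0.87 = 0.724, and the chance of meeting the rule rises from 0.650 to 0.713.

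**The case for a change.** The strongest case does not need a contradiction. Even if Sections 3.0 and 24.0 agree, there is still no rule for a patient withdrawn during the procedure, the team sees the count as it builds, and replacement can only help: it never turns a pass into a fail. Feasibility is the study's stated goal, so a mapping abandoned because the patient could not tolerate it is itself a result and should not drop out of sight. A sentence of protocol text costs almost nothing.

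Much of this stands. The gap is real, the conditional figures are right, and at withdrawal rates of 5-10% the shift would not be trivial.

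Three things limit its force. First, Section 13.0 already requires the reason for each discontinuation to be documented, so an abandoned case is on record and can be shown with the other patients. Second, Section 11.0 counts success only when it comes from mapping-directed ablation; a patient who never had that ablation cannot be a success, and scoring that patient as a non-success among the ten is both available and conservative. Third, no decision, error rate or next step is attached to the success label in this early feasibility study. A reader shown ten or eleven patients with outcomes and reasons can form either count.

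**Conclusion.** No change is needed. The claimed conflict between Sections 3.0 and 24.0 does not hold; they describe the same ten patients, and harmonising their wording would not create the missing rule. What remains is an unwritten detail about an event whose frequency the documents do not give. No rule in the plan produces a wrong result, and ordinary reporting covers the gap: list every patient, give the reason for any abandoned mapping, and count that patient as a non-success.

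The size rests on assumed response rates of 60-70% and an assumed withdrawal rate. At the 2-3% reference the chance of meeting the rule moves by about 3 to 6 percentage points. The 15 to 19 point figures apply only once a withdrawal has occurred; an overall shift of that order would need withdrawal in about one patient in ten. The one-year element has no effect unless loss is assumed to differ by acute response and lost patients are also removed from the acute count, which no section says.

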4.0 Study-Wide Number of Subjects

Not applicable, this study is not a multicenter study.

5.0 Study-Wide Recruitment Methods

Not applicable, this study is not a multicenter study.

6.0 Multi-Site Research

Not applicable, as this is not a multicenter study.

7.0 Study Timelines

The research subjects will be undergoing a clinically-indicated second ablation procedure. On the day of the ablation procedure, the procedure will be utilizing the new mapping technology to identify areas of high EMR and this information will be incorporated into the ablation strategy in conjunction with the other electroanatomic data. As is the usual

clinical routine, patients will be followed every 3-12 months after completion of (or early withdrawal from) study treatment, as clinically indicated, for a minimum of one year.

Upon completion of all study data collection on the 10 participants, primary data analysis will begin.

Follow-up. The patients will undergo standard post ablation follow-up as part of their routine clinical care. As per the Heart Rhythm Society guidelines, following ablation, patients receive some type of post ablation monitoring (Event monitor, Holter monitor, smartphone monitor, Implantable loop recorder-LINQ). This choice of monitoring will be made by the patient's physician in conjunction with the patient based on clinical need. The follow-up schedule will also be determined based on patient and clinical need, and the guidelines. The following table presents an idealized version of the follow-up schedule, but this will be adjusted based on clinical need.

	Screening	Day 0	5-28 days post	2-4 months post	4-8 ³ months	10-14 months
H&P	X	X	X	X	X	X
ECG	X	X	X	X	X	X
Labs	X ⁴	X ⁵				
Monitoring ¹					X	X
Device Interrogation ²	X	X	X	X	X	X

1 Monitoring information will be collected if ordered for standard clinical care. This includes Ambulatory monitoring (Holter), Event Monitor, SmartPhone Monitor

2 Device Interrogation will be performed as part of standard clinical care. This includes implantable loop recorder (LINQ), pacer or defibrillator, if the patient has a device

3 If a patient does not have an office visit in this window, a phone follow-up will be obtained.

4 Labs are clinically indicated and include basic metabolic panel for screening

5 Labs are clinically indicated and include basic metabolic panel, CBC and coagulation panel and may be performed within 3 weeks prior to the procedure

